sc	subcutaneous(ly)
SD	standard deviation
SE	standard error
SF-12	12-Item Short-Form Health Survey

Statistical Analysis Plan

Abbreviation	Term			
SI	standard international			
SOC	system organ class			
SOP	tandard operating procedure			
ULN	upper limit of normal			
WHO Drug	World Health Organization Drug Dictionary			
WPAI	Work Productivity and Activity Impairment			

INTRODUCTION

This statistical analysis plan (SAP) describes the planned analysis and reporting for Teva Branded Pharmaceutical Products R&D, Inc. Study TV48125-CNS-30058, (a multicenter, double-blind, double-dummy study to explore the long-term safety and efficacy of TEV-48125 for the prevention of cluster headache), and was written in accordance with GSD-SOP_702 (Statistical Analysis Plan).

The reader of this SAP is encouraged to read the study protocol for details on the conduct of this study, the operational aspects of clinical assessments, and the timing for completing the participation of a patient in this study.

The SAP is intended to be in agreement with the protocol. However, the SAP may contain more details regarding these particular points of interest, or other types of analyses (eg, other endpoints). When differences exist in descriptions or explanations provided in the study protocol and this SAP, the SAP prevails; the differences will be explained in the clinical study report.

1. STUDY ENDPOINTS

1.1. Primary Objective and Endpoints

The primary objective of this study is to evaluate the long-term safety of fremanezumab in adult patients with cluster headache (CH).

Safety endpoints are as follows:

- occurrence of adverse events throughout the study
- changes from baseline (day 0 of the Phase 3 pivotal efficacy studies) in clinical laboratory (serum chemistry, hematology, coagulation, and urinalysis) test results
- changes from baseline (day 0 of the Phase 3 pivotal efficacy studies) in vital signs (pulse, systolic and diastolic blood pressure, and oral temperature) measurements

 Note: Oxygen saturation will be measured in cases of suspected anaphylaxis and severe hypersensitivity. Respiratory rate will also be measured in these cases but not as a standard vital sign.
- abnormal standard 12-lead electrocardiogram (ECG) findings
- clinically significant changes in physical examination, including body weight
- occurrence of injection site reactions (ie, erythema, induration, and ecchymosis) and/or injection site pain
- occurrence of anaphylaxis and hypersensitivity reactions
- use of concomitant medications during the study
- suicidal ideation and behavior as measured by the electronic Columbia Suicide Severity Rating Scale (eC-SSRS)

1.2. Secondary Objective and Endpoints

There are no secondary objectives and secondary endpoints in this study.

[figure not shown]
1.3. Immunogenicity Objective and Endpoints

The immunogenicity objective is to evaluate the immunogenicity of fremanezumab and the impact of antidrug antibodies (ADAs) on clinical outcomes in patients exposed to fremanezumab.

The immunogenicity endpoints are ADA incidence and characteristics (eg, titer, kinetics, and neutralizing activities).

1.4. Exploratory Efficacy Endpoints

Exploratory efficacy endpoints are:

2. STUDY DESIGN

2.1. General Design

This is a 68-week extension study to evaluate the long-term safety and efficacy of fremanezumab in adult patients with CH. During the course of any CH attack, patients will be allowed to use acute medications to treat acute headaches, as needed.

Upon completion of the final study assessments, early withdrawal from the study, or discontinuation for any reason, patients will be offered the opportunity to enter a 32-week long-term safety study (as described in the study protocol of TV48125-CNS-30058) for safety and ADA evaluation without additional dosing. Patients who satisfactorily complete the study may be offered to enroll the long-term safety study TV48125-CNC-30058 for 68 weeks (as described in the study protocol) to receive additional dosing and a final follow-up visit for safety and ADA evaluation. In any case, during the period of the long-term safety study, where patients are not receiving additional dosing (and are waiting for ADA evaluation), these patients should be treated with standard of care as appropriate.

It was planned that 360 eligible patients with ECH and CCH rolling over from the pivotal studies (Studies TV48125-CNS-30056 and TV48125-CNS-30057, respectively) will receive fremanezumab during this study.

[figure not shown]
The end of study is defined as the date the last patient attends the follow-up visit.

The study duration will be for approximately 42 months from Q1/2017 to Q2/2020. Note, the study is completed Q2/2019 due to early terminations of pivotal Studies TV48125-CNS-30056 and TV48125-CNS-30057.

The study schematic diagram for patients enrolling in this study for the purpose of evaluating the long-term safety and efficacy of fremanezumab is presented in Figure 1.

Study procedures and assessments with their timing are summarized in Table 4 of the study protocol (patients enrolling in this study from the pivotal efficacy studies) and Table 5 of the study protocol (patients rolling over from the pivotal efficacy studies for evaluation of ADAs, adverse events, and concomitant medications only).

Figure 1: Overall Study Schematic Diagram

- ^a The run-in period for patients with ECH lasted at least 7 days (+3 days), and the run-in period for patients with CCH lasted at least 28 days (+3 days).
- ^b Screening will occur at visit 1 of the Phase 3 pivotal efficacy studies.
- c Visit 1 of this study corresponds to the EOT visit (visit 5) of the pivotal efficacy studies. The EOT visit procedures/assessments for the pivotal efficacy study must be completed before beginning visit 1 procedures/assessments. EOT visit procedures/assessments will not be repeated at visit 1 of this study. The EOT visit procedures/assessments are detailed in the protocols for Studies TV48125-CNS-30056 and TV48125-CNS-30057.

CCH=chronic cluster headache; ECH=episodic cluster headache; EOT=end-of-treatment; iv=intravenous; pts=patients; sc= subcutaneous; V=visit; W=week.

Note: Up to 600 patients from the Phase 3 pivotal efficacy studies (Studies TV48125-CNS-30056 and TV48125-CNS-30057) are expected to enroll in this study.

2.2. Randomization and Blinding

This is a double-blind study; blinding will be retained from the pivotal studies and throughout this long-term safety extension study. Patients will be assigned to treatments as described in Table 1 and Section 5.1.1.1 of the study protocol based on their randomization in the pivotal studies (Studies TV48125-CNS-30056 and TV48125-CNS-30057).

2.3. Data Monitoring Committee

Not applicable.

2.4. Sample Size and Power Considerations

There are no statistical considerations for the sample size. Up to 600 patients from the Phase 3 pivotal efficacy studies (Studies TV48125-CNS-30056 and TV48125-CNS-30057) are expected to enroll in this study.

2.5. Sequence of Planned Analyses

2.5.1. Planned Interim Analyses

Not applicable.

2.5.2. Final Analyses and Reporting

All analyses identified in this SAP will be performed after the final database lock for study completion. The study will be unblinded after the pivotal studies (TV48125-30056 and TV48125-30057) are completed and unblinded.

3. ANALYSIS SETS

3.1. Enrolled Patients

[figure not shown]
The enrolled patients will include all patients who are enrolled in the study for any reason.

3.2. Intent-to-Treat Analysis Set

The intent-to-treat (ITT) analysis set will include all patients who are enrolled in this study for additional fremanezumab treatment and long-term safety evaluation, regardless if they receive study treatment or not.

This analysis set does not include patients who are enrolled in this study for the evaluation of ADA and safety only.

3.3. Safety Analysis Set

4. GENERAL ISSUES FOR DATA ANALYSIS

4.1. General

Descriptive statistics for continuous variables include count (n), mean, standard deviation (SD), standard error (SE), median, minimum, and maximum. In addition, for fremanezumab concentration percentage coefficient of variation (%CV) and geometric mean will also be calculated. Descriptive statistics for categorical variables include patient counts and percentages, and a missing category will be displayed as appropriate.

Summaries of potentially clinically significant abnormal values for clinical laboratory tests and vital signs values will include all postbaseline values (including scheduled, unscheduled, and early withdrawal visits).

4.2. Specification of Baseline Values

Baseline values will be the baseline values from the pivotal studies for both safety analyses.

4.3.

4.4. Study Days and Visits

For by-visit summaries, if there are multiple assessments at a postbaseline visit then the last non-missing assessment at that visit will be used for the summary (this includes scheduled and unscheduled assessments), except for triplicate ECG assessments (see Section 8.11 for further details).

Study visits for patients who are enrolled the study for full study assessments are in Table 2. Study procedures and assessments are detailed in the Table 4 of the study protocol.

Table 2: Study Visits for Treated Patients

Double-blind treatment period							Follow-up period					
Visit #	V1	V2	V3	V4	V5	V6	V7	V8	V9	V10	V11	V12
Week	0	4	8	12	16	20	24	28	32	36	40	68
											EOT/early withdrawal	

Notes: Visit 1 of the current study corresponds with the EOT visit (visit 5) of the pivotal efficacy studies. The EOT visit procedures/assessments are detailed in the protocols for Studies TV48125-CNS-30056 and TV48125-CNS-30057. EOT=end of treatment.

Study visits and assessments for patients who are enrolled in the study for the purpose of evaluating ADAs and safety only are detailed in Table 3.

Table 3: Study Visits and Assessments for Patients Enrolled in the Study for Evaluation of Antidrug Antibodies and Safety (Adverse Events and Concomitant Medications) Only

Procedures and assessments	Enrollment visit	Follow-up visit		
	Visit 1 ^a	Visit 12		
	Day 0	Approximately 7.5 months (approximately 5 half-lives of the IMP) after the last dose of the IMP during the pivotal efficacy study		
Informed consent	X			
Adverse events b	X	X		
Concomitant medication inquiry	X	X		
Blood sample for ADA analysis		X		

^a Visit 1 of the current study corresponds with the EOT visit/early withdrawal visit of the pivotal efficacy studies. EOT visit procedures/assessments must be completed before the patient begins participation in this study. The EOT visit procedures/assessments are detailed in the protocols for Studies TV48125-CNS-30056 and TV48125-CNS-30057.

Study days are numbered relative to the first day of the IMP administration in this study. The start of treatment (day 1) is defined as the date on which a patient takes the first dose of the IMP in this study, as recorded on the case report form (CRF). Days will be numbered relative to treatment start (ie, ..., -2, -1, 1, 2, ...; with day 1 being the first day of the IMP administration and day -1 being the day before the first day of the IMP administration).

b Patients will return for unscheduled visits in the event of any safety concern.

ADA=antidrug antibody; EOT=end-of-treatment; IMP=investigational medicinal product.

^{&#}x27;Last Assessment' may be derived for analysis purpose and is defined as the last observed postbaseline data. For patients who withdraw from the study, their data at the early withdrawal visit will be excluded from the by-visit sections but will be included in the Last Assessment section.

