7.4. Clinical Laboratory Tests

All clinical laboratory test results outside of the reference range will be judged by the investigator as belonging to one of the following categories:

- abnormal and not clinically significant
- abnormal and clinically significant

A laboratory test result that is judged by the investigator as clinically significant will be recorded on the source documentation, transcribed to the CRF as an adverse event, and monitored as described in Section 7.1.2. An event may include a laboratory or diagnostic test abnormality (once confirmed by repeated testing) that results in the withdrawal of the patient from the study, the temporary or permanent cessation of treatment with IMP or medical treatment, or further diagnostic workup. (Note: Abnormal laboratory or diagnostic test results at the screening visit that preclude a patient from entering the study or receiving IMP are not considered adverse events.)

In addition, potentially clinically significant values may be predefined by the sponsor for selected laboratory test variables and, if so, will be documented in the statistical analysis plan or other relevant documents (eg, medical monitoring plan or laboratory analysis plan).

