7.6. Vital Signs

Vital signs (blood pressure [systolic/diastolic], body temperature, and pulse) will be measured before other assessments (eg, blood draws and administration of questionnaires) at the time points detailed in [Table 4](#). All vital signs results outside of the reference ranges will be judged by the investigator as belonging to one of the following categories:

- abnormal and not clinically significant
- abnormal and clinically significant

Before pulse and blood pressure are measured, the patient must be in a supine or semi-erect/seated position and resting for at least 5 minutes. The same position and arm should be used each time vital signs are measured for a given patient. For any abnormal vital sign finding, the measurement should be repeated as soon as possible. Any vital sign value that is judged by the investigator as a clinically significant change (worsening) from a baseline value will be considered an adverse event, recorded on the source documentation and transcribed onto the CRF, and monitored as described in [Section 7.1.2](#).

In addition, potentially clinically significant values may be predefined by the sponsor for selected vital signs (see [Section 7.6](#)) and, if so, will be documented in the statistical analysis plan or other relevant documents (eg, medical monitoring plan).

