APPENDIX J. GUIDANCE ON SAFETY MONITORING

Guidance on Monitoring Patients with Elevated Liver Function Tests

Liver enzymes (alanine aminotransferase [ALT], aspartate aminotransferase [AST], gamma-glutamyl transpeptidase [GGT], and alkaline phosphatase [ALP]) as well as total, direct, and indirect bilirubin will be measured at each study visit.

In any case of elevated ALT or AST to a level exceeding $\geq 2 \times$ the upper limit of the normal range (ULN) (including patients whose baseline ALT or AST levels are $\geq 2 \times$ and $\leq 3 \times$ the ULN, who may be enrolled in the study), a thorough medical history and physical examination with a focus on liver disease should be undertaken.² In addition, the patient should be instructed to refrain from alcoholic beverages.

In case of symptoms compatible with drug-induced liver injury during the study, patients will be instructed to return to the investigational center for an unscheduled visit or to go to the emergency room to measure liver enzymes as soon as possible. Solitary elevations of total, direct, or indirect bilirubin, not accompanied by elevations of ALT or AST should be managed according to the discretion of the treating physician.

Elevation of Either ALT or AST to $\geq 3 \times$ ULN

Confirmation is required prior to IMP discontinuation in cases of elevation of either ALT or AST $\geq 3 \times$ ULN. (Note: In cases of elevation of ALT or AST $\geq 8 \times$ the ULN, no confirmation is required prior to IMP discontinuation, but the assessments below should be performed.) The following procedures should be followed:

- The day in which the abnormal value is received from the laboratory will be considered as day 0.
- The investigator should repeat the test for confirmation purposes (this may be performed in a local laboratory along with complete blood cell [CBC] count and differential to assess for eosinophilia; in general, in case a blood sample is sent to a local laboratory, the following assessments [and reference ranges] are mandatory: ALT [serum glutamic pyruvic transaminase], AST [serum glutamic oxaloacetic transaminase], ALP, bilirubin [total, direct, and indirect], CBC [with differential for eosinophil count, separate tube], and international normalized ratio (INR) [separate tube; not to be sent in a confirmatory test]). The investigator should also question the patient regarding symptoms.

The abnormality will be regarded as confirmed in each of the following scenarios:

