8.8. Clinical Laboratory Tests

Clinical laboratory tests (serum chemistry, hematology, coagulation, and urinalysis; see protocol Appendix M) will be performed at visits 4, 7, 10 and 11 using the central laboratory. All clinical laboratory test results outside of the reference range will be judged by the investigator as belonging to one of the following categories:

- abnormal and not clinically significant
- abnormal and clinically significant

A laboratory test result that is judged by the investigator as clinically significant will be recorded on the source documentation and the CRF as an adverse event, and monitored as described in Section 7.1.2 of the protocol.

Laboratory test results will be presented in standard international (SI) units in summaries. Laboratory values and changes from baseline to each visit and Last Assessment will be summarized using descriptive statistics. Shifts (below [low], within [normal], and above [high] the normal range) from baseline to each postbaseline visit and the Last Assessment will be summarized using patient counts. Baseline is defined as the last observed data before the administration of the first dose of the IMP in the pivotal study.

The potentially clinically significant abnormal values will be derived using criteria specified in Table 4 based on all postbaseline values (including scheduled, unscheduled, and withdrawal visits). The overall incidence of potentially clinically significant abnormal values will be summarized for laboratory variables using descriptive statistics by treatment group. Listings for patients who have potentially clinically significant abnormal laboratory data will be presented.

Table 4: Criteria for Potentially Clinically Significant Laboratory Values

Test		Criterion value
Serum chemistry		
ALT		≥3x ULN
AST		≥3x ULN
ALP		≥3x ULN
GGT		≥3x ULN
LDH		≥3x ULN
BUN		≥10.71 mmol/L
Creatinine		≥177 µmol/L
Bilirubin (total)		≥34.2 µmol/L
Hematology		
Hematocrit	Men	<0.37 L/L
	Women	<0.32 L/L
Hemoglobin	Men	≤115 g/L
	Women	≤95 g/L
WBC counts		≤3 x 10 ⁹ /L
		≥20 x 10 ⁹ /L
Eosinophils		≥10%
ANC		$\leq 1 \times 10^9/L$
Platelet counts		≤75 x 10 ⁹ /L
		≥700 x 10 ⁹ /L
Urinalysis		
HGB		≥2 unit increase from baseline
Glucose		≥2 unit increase from baseline
Ketones		≥2 unit increase from baseline
Total protein		≥2 unit increase from baseline

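### Letting unscheduled repeats replace scheduled values in by-visit tables can make the laboratory shift tables look nearer normal than the scheduled results were, probably by a small amount

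*SAP*

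**What the plan says.** SAP 4.4 sets the rule for tables that report results visit by visit: "if there are multiple assessments at a postbaseline visit then the last non-missing assessment at that visit will be used for the summary". A parenthesis gives its scope: "this includes scheduled and unscheduled assessments), except for triplicate ECG assessments".

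SAP 8.8 then plans "Shifts (below [low], within [normal], and above [high] the normal range) from baseline to each postbaseline visit and the Last Assessment". No laboratory shift to a worst value is planned. Last Assessment "is defined as the last observed postbaseline data" (SAP 4.4), so a repeat can supply that value too.

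The protocol ties repeats to abnormal results in three places:
- Vital signs (protocol 7.6): "For any abnormal vital sign finding, the measurement should be repeated as soon as possible".
- ALT or AST at or above 3 x ULN (protocol Appendix J): "The investigator should repeat the test for confirmation purposes". If the elevation is confirmed at 3 to below 5 x ULN, further draws follow around days 5, 8, 14 and 28.
- Laboratory tests in general (protocol 7.4): "An event may include a laboratory or diagnostic test abnormality (once confirmed by repeated testing". This mentions confirmation but does not require a repeat of every abnormal result.

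Two parts of the SAP work differently. PCS laboratory and vital-sign summaries use all postbaseline values, scheduled or not (SAP 4.1, 8.8, 8.10). ECG findings use the worst value at a visit, with a shift to the patient's worst value overall (SAP 8.11).

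**The concern.** A last-value rule does no harm when repeats are unrelated to the result. Here many repeats happen because the first value was abnormal, and no matching repeat is called for when it was normal. For those repeats, selection runs one way: an abnormal reading may be exchanged for a later one that has drifted back by chance or recovered, while normal readings stay as they are.

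Laboratory changes from baseline are among the primary safety endpoints (SAP 1.1), and protocol 1.3.1 lists liver enzyme elevations as a potential risk. The PCS tables do not fill the whole gap. SAP Table 4 starts at 3 x ULN for ALT, AST, ALP, GGT and LDH. It has no criterion for sodium, potassium, calcium, magnesium, phosphate, serum glucose, albumin or INR, all of which protocol Appendix M lists. For those tests, and for liver values between 1 and 3 x ULN, the shift table is the only planned categorical summary of the laboratory values in the visible SAP.

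**Working it through.** The documents give no figure for this, so there is nothing of the plan's to reproduce. The check covers direction, then size under stated assumptions.

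**Direction.** Let p be the share above the limit at the scheduled draw, r the chance that an abnormal value is repeated at the same visit, and s the chance that the repeat is still abnormal. If only abnormal values are repeated, the tabulated share is

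p x [1 - r(1 - s)].

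This equals p when r = 0 or s = 1 and is otherwise lower. If everyone were repeated, the share would stay at p, so the selective trigger causes the loss.

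**Size.** None of p, r or s is in the documents. Assume p = 2.5% (the upper tail of a 95% reference range) and bivariate normal first and repeat values with correlation 0.7, 0.8 or 0.9. The chance that both exceed the limit is 0.83%, 1.10% or 1.48%, so s = 0.83/2.5 = 0.33, 1.10/2.5 = 0.44 or 1.48/2.5 = 0.59.

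| Share of abnormal values repeated (r) | Correlation 0.7 | Correlation 0.8 | Correlation 0.9 |
|---|---|---|---|
| 10% | 2.3% | 2.4% | 2.4% |
| 30% | 2.0% | 2.1% | 2.2% |
| 100% | 0.8% | 1.1% | 1.5% |

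For example, with r = 0.3 and s = 0.33, 2.5% x [1 - 0.3 x 0.67] = 2.0%.

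**The one explicit laboratory trigger.** Suppose ALT varies lognormally about a true level of k x ULN, with within-person CV c (assumed 20% to 50%). The chance that a prompt repeat is at or below ULN is Φ(-ln k / σ), where σ = √ln(1 + c²). For c = 50%, σ = 0.47. This gives about 1% for k = 3 and 7% for k = 2. For c = 20% and k = 2 it is 0.02%. A prompt confirmatory repeat would therefore seldom turn a high into a normal. Later follow-up draws could, if they are assigned to the same visit.

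**Mean change.** Take systolic pressure with assumed mean 130, between-patient SD 12 and within-visit SD 8 mm Hg, and every reading above 140 repeated once. In simulation the last-value rule lowers the mean by 1.4 mm Hg. If baseline is also the last value taken, as SAP 8.10 defines it, and the same repeat practice applied then, most of this cancels: a true change of +4 shows as about +3.8.

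**The case against.** The strongest case against is that the triggers and the tables barely meet. The only instruction to repeat every abnormal finding is for vital signs, which have mean changes and PCS incidence but no shift table (SAP 8.10). The one explicit laboratory trigger, ALT or AST at or above 3 x ULN, meets a PCS criterion, so those values are counted and listed whatever the repeat shows. They are also adverse events of special interest, as is INR above 1.5 (protocol 7.1.7). Results that the investigator judges clinically significant become adverse events. The rule covers assessments at a visit, and the visible SAP does not assign day 5 to day 28 draws, or local-laboratory repeats, to a scheduled visit. No inferential analysis is planned. All of this stands, and it limits the exposure to milder values and tests without a PCS criterion, repeated at the investigator's discretion.

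Three stronger readings are tempting, and the documents do not support them:
- A reader might infer that most highs vanish. The bottom row of the table does imply a loss of 41% to 67% (1 - 1.48/2.5 and 1 - 0.83/2.5), but only if every out-of-range laboratory value is repeated, which the protocol does not require.
- A reader might infer that the rule can move results only towards normal. Appendix J also calls for unscheduled liver tests when symptoms suggest liver injury, and Appendix B allows unscheduled visits at the patient's request. Either can replace a normal scheduled value with an abnormal one.
- A reader might infer that serious liver signals are lost. The PCS and special-interest displays keep them.

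**Conclusion.** The point holds in limited form. Where a repeat at the same visit was prompted by an abnormal result, SAP 4.4 can replace that result with one nearer normal, and the laboratory shift tables can then understate abnormality. No worst-value laboratory shift guards against this, although ECG findings have one.

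The size cannot be determined from the documents and is probably small: about 0.1 to 0.5 percentage points off a true 2.5% if 10% to 30% of abnormal values are repeated. That range rests on the assumed correlation of 0.7 to 0.9, on normality, and on the repeat being assigned to the same visit. Mean changes are hardly affected. This is a cheap improvement rather than a flaw that undermines the safety conclusions.

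**What to change.** - **SAP 4.4:** for by-visit summaries and shifts, use the scheduled assessment at the visit, and use a repeat or unscheduled value only if the scheduled one is missing. State how unscheduled and local-laboratory results map to visits.
- **SAP 8.8:** add a shift from baseline to the worst postbaseline value over all scheduled and unscheduled results, as SAP 8.11 already does for ECG findings. Low and high are both abnormal, so show the lowest and highest values separately. This table is needed beside the first change; otherwise symptom-triggered abnormal results would drop out of the shift displays.
- **PCS summaries:** keep the all-values rule as it is.

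The cost is a few SAP sentences, a changed selection flag in programming and one extra shift table. Data collection and study conduct do not change.
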